9.5. Events of Clinical Interest

Not applicable.

9.6. Emergency Unblinding of Treatment Assignment

Not applicable.

9.7. Pregnancy

Pregnancy, in and of itself, is not regarded as an AE unless there is suspicion that the study cream may have interfered with the effectiveness of a contraceptive medication or method. When a pregnancy has been confirmed in a participant during maternal or paternal exposure to study cream, the following procedures should be followed in order to ensure safety:

- The study cream must be discontinued immediately (female participants only).
- The investigator must complete and submit the Incyte Clinical Trial Pregnancy Form to the sponsor or its designee within **24 hours** of learning of the pregnancy.

Data on fetal outcome are collected for regulatory reporting and drug safety evaluations. Follow-up should be conducted for each pregnancy to determine outcome, including spontaneous or voluntary termination, details of the birth, and the presence or absence of any birth defects, congenital abnormalities, or maternal and/or newborn complications, by following until the first well-baby visit. Pregnancy should be recorded on a Clinical Trial Pregnancy Form and reported by the investigator to the sponsor or its designee. Pregnancy follow-up information should be recorded on the same form and should include an assessment of the possible causal relationship to the sponsor's study cream to any pregnancy outcome, as well as follow-up to the first well-baby visit or the duration specified in local regulations, whichever is later. Refer to the Incyte Reference Guide for Completing the Clinical Trial Pregnancy Form.

Any SAE occurring during the pregnancy of a study participant must be recorded and reported as described in Section 9.4.

Abnormal pregnancy outcomes (eg, spontaneous abortion, fetal death, stillbirth, congenital anomalies, or ectopic pregnancy) are considered SAEs (if occurring in the study participant) and must be reported as described in Section 9.4. If an abnormal pregnancy outcome is reported in a study participant's partner, the event should be reported to the sponsor on the Clinical Trial Pregnancy Form.

9.8. Warnings and Precautions

Special warnings or precautions for the study cream, derived from safety information collected by the sponsor or its designee, are presented in the IB. Additional safety information collected between IB updates will be communicated in the form of Investigator Notifications. Any important new safety information should be discussed with the participant during the study as necessary. If new significant risks are identified, they will be added to the ICF/assent.

9.9. Product Complaints

The sponsor collects product complaints on study drugs and drug delivery systems used in clinical studies in order to ensure the safety of study participants, monitor quality, and facilitate process and product improvements.

All product complaints associated with material packaged, labeled, and released by the sponsor or its designee will be reported to the sponsor. All product complaints associated with other study material will be reported directly to the respective manufacturer.

The investigator or their designee is responsible for reporting a complete description of the product complaint via email or other written communication to the sponsor contact or respective manufacturer as noted in the packaging information. Any AE associated with a product complaint should be recorded as described in Section 9.3.

If the investigator is asked to return the product for investigation, they will return a copy of the product complaint communication with the product.

9.10. Treatment of Excessive Use

There has been no clinical experience with overdose resulting from excessive use of ruxolitinib cream. Treatment of excessive use should consist of general supportive measures.

10. STATISTICS

10.1. Sample Size Determination

Approximately 100 participants will be enrolled. The study is not powered for statistical comparison but instead is based on the evaluation of safety. This sample size will provide > 99% chance of detecting at least 1 AE of interest if the underlying AE rate is 5%, and therefore it is anticipated that sufficient data for safety investigation will be permitted. As this is an open-label study, all participants will be treated with ruxolitinib 1.5% cream.

10.2. Populations for Analyses

The populations for analysis are provided in Table 11.

Table 11: Populations for Analysis

Population	Description
FAS	The FAS will include all participants enrolled in the study who applied study cream at least once. The FAS will be used for the summary of demographics, baseline characteristics, participant disposition, and all analyses of efficacy and safety data.
PK/hematology lab evaluable	The PK evaluable population will include all participants who applied study cream at least once and provided at least 1 postbaseline PK sample (1 PK measurement). The hematology lab evaluable population will include all participants who applied study cream at least once, provided the baseline hematology blood sample, and at least 1 postbaseline hematology blood sample (1 hematology measurement). The PK/hematology lab evaluable population will include all participants who are both PK evaluable and hematology lab evaluable.

10.3. Level of Significance

This is a safety study. No formal hypotheses will be tested; all efficacy analyses are exploratory.

10.4. Statistical Analyses

10.4.1. Primary Analysis

A TEAE is any AE either reported for the first time or worsening of a pre-existing event after first application of study cream and up to 30 days after the last application of study cream. Analysis of AEs will be limited to TEAEs, but data listings will include all AEs regardless of their timing in relation to study cream application. Treatment-emergent AEs will be tabulated by the MedDRA preferred term and system organ class. Severity of AEs will be based on CTCAE v5.0 using Grades 1 through 5.

The subset of AEs considered by the investigator to have a relationship to study cream will be considered to be treatment-related AEs. If the investigator does not specify the relationship of the AE to study cream, then the AE will be considered treatment-related. The incidence of TEAEs, treatment-related TEAEs, serious TEAEs, Grade 3 or higher TEAEs, and TEAEs leading to

study cream interruption or study discontinuation will also be tabulated. A summary of primary endpoint analyses is provided in Table 12.

Table 12: Summary of Primary Endpoint Analyses

Endpoint	Population	Treatment	Population-Level Summary Metric
Incidence of TEAEs, treatment-related TEAEs, serious TEAEs, Grade 3 or higher TEAEs	FAS	Ruxolitinib 1.5% BID cream	Rate of TEAEs
Incidence of TEAEs leading to study cream interruption or study discontinuation	FAS	Ruxolitinib 1.5% BID cream	Rate of TEAEs
Incidence of TEAEs summarized by Grades of AE	FAS	Ruxolitinib 1.5% BID cream	Rates of TEAEs

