2.3. Benefit/Risk Assessment

In the Phase 3 AD studies, ruxolitinib 1.5% cream BID rapidly and effectively improved both the signs and symptoms of AD in adults and adolescents, being statistically significantly superior to vehicle cream BID at the end of the vehicle-controlled period (Week 8) for IGA-TS, EASI75, and ≥ 4-point improvement in Itch NRS score. The antipruritic effect of ruxolitinib 1.5% cream BID showed a rapid onset with evidence of a treatment effect on daily Itch NRS scores as early as Day 1 (ie, within 12 hours after the first application of study cream). The disease course (assessed by IGA scores and %BSA affected by AD at study visits during Weeks 8 through 52) was well-controlled throughout the entirety of the LTS period of the study. The treatment effects of ruxolitinib 1.5% cream BID on IGA-TS, EASI75, and Itch NRS score were consistently observed across both adult and adolescent subgroups.

Safety data from the Phase 3 AD studies demonstrated that use of ruxolitinib 1.5% cream BID continuously for 8 weeks followed by prolonged (44 weeks) intermittent use was safe and well-tolerated. The TEAEs were generally Grade 1 or 2 in severity and were most often events of nasopharyngitis and upper respiratory tract infection. Frequencies of these events were within the expected range for the general AD population. There were no meaningful differences in the TEAE profile of ruxolitinib 1.5% cream BID between the adult and adolescent subgroups.

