## 1. INTRODUCTION

This is an open-label, 1-year safety study with an LTS period. Adolescents aged  $\geq 12$  to  $< 18$  years with AD for at least 2 years and affecting 3% to 20% BSA (excluding the scalp) plus a total IGA score of 2 or 3. The primary purpose of this study is to collect additional long-term safety data regarding the types, severity, and frequencies of TEAEs occurring in adolescents with AD who are treated with ruxolitinib 1.5% cream BID.

The purpose of this SAP is to provide details of the statistical analyses that have been outlined in the INCB 18424-315 Protocol. The scope of this plan includes the final analyses that are planned and will be executed by the Department of Biostatistics or designee and the Department of Clinical Pharmacokinetics or designee will execute the analysis of PK.

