**Table 1: Objectives and Endpoints**

Objectives	Endpoints
Primary	
To evaluate the long-term safety and tolerability of ruxolitinib cream in adolescents with AD.	Incidence of TEAEs, assessed by monitoring the type, frequency, and severity of AEs.
Secondary	
To further evaluate the long-term safety and tolerability of ruxolitinib cream in adolescents with AD.	Changes in vital signs, height, weight, and laboratory data for hematology and serum chemistry.
To characterize the PK of ruxolitinib cream in adolescents with AD.	Trough concentrations of ruxolitinib at each postbaseline visit.
Exploratory	

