### 9.2.2. Adverse Event Summaries

An overall summary of AEs by treatment period will include the following:

- Number (%) of participants who had any TEAEs
- Number (%) of participants who had any ASRs
- Number (%) of participants who had any serious TEAEs
- Number (%) of participants who had any Grade 3 or higher TEAEs
- Number (%) of participants who had any treatment-related TEAEs
- Number (%) of participants who temporarily interrupted ruxolitinib cream because of TEAEs
- Number (%) of participants who permanently discontinued ruxolitinib cream because of TEAEs
- Number (%) of participants who had a fatal TEAE

Subgroup analysis (sex, race, ethnicity) for overall TEAEs will also be provided.

The following summaries will be produced by MedDRA term (if 2 or fewer participants appear in a table, a listing may be appropriate):

- Summary of TEAEs by MedDRA SOC and PT
- Summary of TEAEs by MedDRA PT in decreasing order of frequency
- Summary of ASRs by MedDRA PT in decreasing order of frequency
- Summary of Grade 3 or higher TEAEs by MedDRA SOC and PT
- Summary of Grade 3 or higher TEAEs by MedDRA PT in decreasing order of frequency
- Summary of serious TEAEs by MedDRA SOC and PT
- Summary of serious TEAEs by MedDRA PT in decreasing order of frequency
- Summary of treatment-related TEAEs by MedDRA SOC and PT
- Summary of treatment-related TEAEs by PT in decreasing order of frequency
- Summary of Grade 3 or higher treatment-related TEAEs by MedDRA SOC and PT
- Summary of treatment-related serious TEAEs by MedDRA SOC and PT
- Summary of TEAEs with a fatal outcome by MedDRA SOC and PT

- Summary of TEAEs leading to ruxolitinib cream dose interruption by MedDRA SOC and PT
- Summary of TEAEs leading to discontinuation of ruxolitinib cream by MedDRA SOC and PT

Subgroup analysis (sex, race, ethnicity) for TEAEs by MedDRA PT will also be provided.

Adverse events of interest will be summarized in the following categories:

- Cytopenias
  - Anemia
  - Thrombocytopenia
  - Neutropenia
- Herpes zoster
- Nonmelanoma skin neoplasms
- Liver function test elevations
- Malignancies
- Major Adverse Cardiovascular Events
- Venous and arterial thromboembolic events
- Thrombocytosis and elevated mean platelet volume

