### **11.1. Changes to Protocol-Defined Analyses**

Not applicable.

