3.2.3.2.4	Summary of Treatment-Emergent Adverse Events by MedDRA Preferred Term in Decreasing Order of Frequency in the LTS Period by Ethnicity	LTS-EV
3.2.3.3.1	Summary of Treatment-Emergent Adverse Events by MedDRA Preferred Term in Decreasing Order of Frequency From Baseline to Week 52	FAS
3.2.3.3.2	Summary of Treatment-Emergent Adverse Events by MedDRA Preferred Term in Decreasing Order of Frequency From Baseline to Week 52 by Sex	FAS
3.2.3.3.3	Summary of Treatment-Emergent Adverse Events by MedDRA Preferred Term in Decreasing Order of Frequency From Baseline to Week 52 by Race	FAS
3.2.3.3.4	Summary of Treatment-Emergent Adverse Events by MedDRA Preferred Term in Decreasing Order of Frequency From Baseline to Week 52 by Ethnicity	FAS
3.2.3.4.1	Summary of Application Site Reactions by MedDRA Preferred Term in Decreasing Order of Frequency in the CT Period	FAS
3.2.3.4.2	Summary of Application Site Reactions by MedDRA Preferred Term in Decreasing Order of Frequency in the LTS Period	LTS-EV
3.2.3.4.3	Summary of Application Site Reactions by MedDRA Preferred Term in Decreasing Order of Frequency From Baseline to Week 52	FAS
3.2.4.1	Summary of Grade 3 or Higher Treatment-Emergent Adverse Events by MedDRA System Organ Class and Preferred Term in the CT Period	FAS
3.2.4.2	Summary of Grade 3 or Higher Treatment-Emergent Adverse Events by MedDRA System Organ Class and Preferred Term in the LTS Period	LTS-EV
3.2.4.3	Summary of Grade 3 or Higher Treatment-Emergent Adverse Events by MedDRA System Organ Class and Preferred Term from Baseline to Week 52	FAS
3.2.5.1	Summary of Grade 3 or Higher Treatment-Emergent Adverse Events by MedDRA Preferred Term in Decreasing Order of Frequency in the CT Period	FAS
3.2.5.2	Summary of Grade 3 or Higher Treatment-Emergent Adverse Events by MedDRA Preferred Term in Decreasing Order of Frequency in the LTS Period	LTS-EV
3.2.5.3	Summary of Grade 3 or Higher Treatment-Emergent Adverse Events by MedDRA Preferred Term in Decreasing Order of Frequency From Baseline to Week 52	FAS

Table No.	Title	Population
3.2.6.1	Summary of Serious Treatment-Emergent Adverse Events by MedDRA System Organ Class and Preferred Term in the CT Period	FAS
3.2.6.2	Summary of Serious Treatment-Emergent Adverse Events by MedDRA System Organ Class and Preferred Term in the LTS Period	LTS-EV
3.2.6.3	Summary of Serious Treatment-Emergent Adverse Events by MedDRA System Organ Class and Preferred Term From Baseline to Week 52	FAS

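### The protocol names TEAE incidence by CTCAE grade as a primary-endpoint analysis, but the SAP plans no output for it and declares no change

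*Protocol*

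**What the plan says.** The primary endpoint has the same wording in both documents: "Incidence of TEAEs, assessed by monitoring the type, frequency, and severity of AEs". The SAP Introduction also puts severity into the purpose of the study, which is to collect data on the "types, severity, and frequencies of TEAEs occurring in adolescents with AD".

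Protocol 10.4.1 fixes the scale: "Severity of AEs will be based on CTCAE v5.0 using Grades 1 through 5". Its Table 12 then lists three primary-endpoint analyses, all in the FAS:

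- Row 1: any, treatment-related, serious, and Grade 3 or higher TEAEs.
- Row 2: TEAEs leading to cream interruption or study discontinuation.
- Row 3: "Incidence of TEAEs summarized by Grades of AE".

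SAP 9.2.2 lists the planned AE summaries. The grade line in the overall summary is "Number (%) of participants who had any Grade 3 or higher TEAEs". The grade-based tables by MedDRA term follow the same cut, for example "Summary of Grade 3 or Higher Treatment-Emergent Adverse Events by MedDRA System Organ Class and Preferred Term in the CT Period". Fatal TEAEs have their own line and tables. SAP 11.1, "Changes to Protocol-Defined Analyses", is marked as not applicable.

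**The concern.** Row 3 is listed separately from row 1, and row 1 already contains the Grade 3 or higher cut. Row 3 must therefore mean something more, namely incidence across the grades. No AE output in the SAP provides this, and a reader of SAP 11.1 would conclude that nothing protocol-defined had been dropped.

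The study is descriptive, with one group and no hypothesis test, and it is a post-marketing requirement. The TEAE tables are therefore the primary result. Tolerability is part of the primary objective, and Protocol 9.3 distinguishes Grade 1 (no treatment indicated) from Grade 2 (some treatment indicated, or daily activities limited). In the earlier Phase 3 studies, according to Protocol 2.3, "The TEAEs were generally Grade 1 or 2 in severity". If that pattern recurs, most of the severity information will lie where the planned tables make no distinction.

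**Working it through.** The point is a cross-check of planned outputs, not a calculation. The only figure in the protocol's sample-size section is a greater than 99% chance of seeing at least one event at a true rate of 5% with about 100 participants. It reproduces, since 1 − 0.95^100 = 0.994, but has no bearing here.

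**Step 1. Table 12 against the SAP outputs.**

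| Protocol Table 12 | SAP 9.2.2 and Appendix A | Match |
|---|---|---|
| Row 1: any, related, serious, Grade 3 or higher | Tables 3.2.1 to 3.2.11 | Yes |
| Row 2: interruption of cream, discontinuation of study | Tables 3.2.13 and 3.2.14 (interruption and discontinuation of cream) | Interruption yes; discontinuation defined differently |
| Row 3: TEAEs by grade | None | No |

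**Step 2. Every severity display for AEs.** Tables 3.2.4, 3.2.5 and 3.2.10 and Listing 2.7.7 are Grade 3 or higher. Tables 3.2.12 and Listing 2.7.5 are fatal events. The overall summaries (Tables 3.2.1) carry one line for each of these two cuts. Displays across CTCAE grades exist only for laboratory values (Tables 3.3.3 and 3.3.4).

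**Step 3. What can be recovered from the planned tables.** In one overall summary, let T be the number of participants with any TEAE, S the number with any Grade 3 or higher TEAE, and F the number with a fatal TEAE (Grade 5 under Protocol 9.3).

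- T − S = worst grade 1, 2 or unknown, pooled
- S − F = worst grade 3 or 4, pooled
- F = Grade 5

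A full display would have six categories (1, 2, 3, 4, 5, unknown). The planned tables support three, and two of those appear only if the reader does the subtraction. Four of the five grades cannot be obtained individually.

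**Step 4. Two signs that the SAP is incomplete here.** SAP 9.2.1 assigns unresolved missing severity to an unknown category, yet no planned AE table has a place to show it. Protocol 9.3 has each change in severity between visits reported as a separate AE, so one episode can produce several records at different grades. Incidence by grade therefore needs a counting rule, and the SAP gives none.

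**Step 5. Row 2.** Protocol 7.1.1 and 7.1.2 let a participant stop the cream and stay in follow-up, so stopping the cream and leaving the study are different events. SAP 9.2.2 counts TEAEs leading to the first only, and SAP 11.1 does not mention the difference.

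**The case against.** The strongest reply is that this is a gap in documentation. A grade is recorded for every AE, Listing 2.7.1 covers all AEs, and a by-grade table can be made at any time from existing data. Appendix A calls its lists guidelines, refers to Standard Safety Tables v1.6, and allows list changes without an amendment. Sample displays sit in a separate document. The unknown-severity rule may mean that a severity table was intended.

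Much of this stands: no data are lost, nothing is biased, and a by-grade table may yet be produced. It does not remove the mismatch. The omission is in the body of SAP 9.2.2 as well as in the appendix. The standard tables are cited for their conventions, and their content is not in the documents. A listing is not the rate that Table 12 specifies.

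A reader might infer more than the documents support, in three ways:

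- That severity below Grade 3 goes wholly unreported. It does not: the pooled count follows from two lines of the same summary.
- That Grade 3 or higher is the only cut. The fatal tables give Grade 5.
- That nearly all TEAEs here will be Grade 1 or 2, leaving the Grade 3 or higher tables almost empty. Protocol 2.3 says generally, and describes earlier studies. The documents give no TEAE rate for this study, so any stated share of participants affected would be an assumption.

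On row 2, SAP 6.2 and Tables 1.1.2.1 and 1.1.2.2 do summarise withdrawal from the study with its primary reason. What is missing is a count of TEAEs leading to that withdrawal.

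**Conclusion.** The protocol and SAP disagree on a named primary analysis. One of the three rows of Table 12 has no planned SAP output, and SAP 11.1 says that nothing changed. As written, the SAP separates neither Grade 1 from Grade 2 nor Grade 3 from Grade 4. This rests on reading row 3 as incidence across Grades 1 to 5, which its separation from row 1 and the scale stated in the same section both support. It also rests on the SAP as published, without the unseen table conventions and sample displays. The point should be corrected because it concerns the primary endpoint and costs little, not because the safety conclusions would otherwise be invalid. The row 2 difference is secondary.

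**What to change.** Add to SAP 9.2.2 and Appendix A at least one FAS table, baseline to Week 52, of TEAEs by maximum CTCAE grade (1, 2, 3, 4, 5, unknown), overall and by SOC and PT. State the counting rule: each participant is counted once per PT at the worst grade, and likewise once within each SOC and in the any-TEAE row. Say where unknown ranks against the known grades.

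That table meets row 3. Versions for the continuous-treatment and long-term safety periods, or for treatment-related TEAEs, are optional, since Table 12 does not ask for them.

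For row 2, either tabulate TEAEs leading to study discontinuation beside those leading to discontinuation of cream, or declare the substitution in SAP 11.1.

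The cost is a short SAP amendment and a few standard tables from data already collected. Sample size and study conduct do not change.

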10.4.2. Secondary Analyses

10.4.2.1. Clinical Laboratory Tests

The clinical laboratory data will be analyzed using summary statistics.

Laboratory test values outside the normal range will be assessed for severity based on the normal ranges for the clinical reference laboratory. The incidence of abnormal laboratory values and shift tables relative to baseline will be tabulated. In addition, distributions of key laboratory parameters may be plotted over time; these values will also be classified into CTCAE toxicity grades and tabulated.

10.4.2.2. Vital Signs

Descriptive statistics and mean change from baseline will be determined for vital signs (blood pressure, pulse, respiratory rate, and body temperature), height, and weight at each assessment time. Vital sign results will be reviewed for clinically notable abnormalities.

10.4.3. Pharmacokinetic Analyses

Descriptive analysis of PK concentration data will be performed by matrix (plasma and saliva), study period, and/or visit, using summary statistics such as, but not limited to, number of observations, mean, STD, minimum, median, maximum, geometric mean, geometric coefficient of variation, and/or empirical percentiles as deemed appropriate.

Additional summaries may also be generated by subgroups such as geographical region, age, %BSA treated, and/or disease severity indices at baseline, as deemed appropriate.

Table 13 summarizes all secondary endpoint analyses.

Table 13: Summary of Secondary Endpoint Analyses

Endpoint	Population	Treatment	Population-Level Summary Metric
Change from baseline in vital signs	FAS	Ruxolitinib 1.5% BID cream	Descriptive statistics and mean change from baseline
Change from baseline in laboratory values	FAS	Ruxolitinib 1.5% BID cream	Descriptive statistics and mean change from baseline
Height	FAS	Ruxolitinib 1.5% BID cream	Descriptive statistics
Weight	FAS	Ruxolitinib 1.5% BID cream	Descriptive statistics
PK concentration	PK evaluable	Ruxolitinib 1.5% BID cream	Descriptive statistics

